3.2 Estimands

An estimand is the target of estimation to address the scientific question of interest posed by a study objective. The 4 attributes of an estimand include the population of interest, endpoint of interest, specification of how intercurrent events are reflected in the scientific question of interest, and the summary for the endpoint.

For all objectives, the population of interest is defined through appropriate inclusion/exclusion criteria to reflect the targeted patient population for approval. Refer to the protocol for inclusion/exclusion criteria.

Intercurrent Events

Intercurrent events are those that occur after treatment initiation and either preclude observation of the endpoint or affect its interpretation. The following will be considered intercurrent events:

- Study drug discontinuation before the time point of interest defining the endpoint.
 - For safety objectives:
 - For AEs, study drug discontinuation is handled with a “while-on-treatment strategy,” i.e., response to treatment prior to the occurrence of the intercurrent event of interest, such that all observed values of the endpoint of interest will be used prior to study drug discontinuation.
 - For all other safety endpoints, study drug discontinuation is handled with a “treatment policy strategy”, i.e., the occurrence of the intercurrent event will be considered irrelevant, such that all observed values of the endpoint of interest will be used regardless of study drug discontinuation.
 - For efficacy objectives:
 - For the NPRS objectives, study drug discontinuation is handled with a “while-on-treatment strategy”.
 - For the Penn-FPS-R, PDI, and PGI-C efficacy objectives, study drug discontinuation is handled with a “treatment policy strategy”.
 - For all other objectives (i.e., use of non-study TN standard of care medications on or before the time point of interest), this intercurrent event will be handled with a “while-on-treatment strategy”

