4.2 Treatment Groups

Treatment groups in the DBT phase are rimegepant 75 mg and placebo. The treatment group in the OLE phase is rimegepant 75 mg.

Populations of treated subjects will be assessed by the as-treated treatment group; i.e., by the treatment actually received. Otherwise, all other populations and all efficacy analyses will be assessed by the as-randomized treatment group. The enrolled population will be assessed overall.

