6.2.3.1 Subject Disposition during the DBT Phase

Subject disposition during the DBT phase will be summarized for treated subjects by as-treated treatment sequence and overall as the number and percentage of subjects in the following categories:

- Completed the first treatment period
- Withdrawn from the first treatment period
 - Reasons for withdrawal, including not reported
- Completed the second treatment period
- Withdrawn from the second treatment period
 - Reasons for withdrawal, including not reported.
- Continuing to the OLE phase
- Not continuing to the OLE phase

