6.3 Efficacy

Unless otherwise noted, the primary and secondary efficacy analyses will be conducted on the mITT population. DBT and OLE efficacy data will be included in listings by subject, treatment sequence and period, study phase and visit (as applicable). Descriptive summary statistics will be provided for DBT and OLE phase data. Statistical analyses outlined in Table 3: Primary and Secondary Efficacy Estimands and Analyses will only be done for the DBT phase data.

Table 3: Primary and Secondary Efficacy Estimands and Analyses

Index	Description	Variable Type	Statistical Model	On-Study Data
Primary Estimand				
P01	Difference between treatment groups in change from baseline in average daily NPRS scores at the end of the randomization phase	Continuous	MMRM	Baseline, Day 14, 21, 35
Secondary Estimand				
S01	Difference between treatment groups in change from baseline in Penn-FPS-R score at the end of the randomization phase	Continuous	MMRM	Baseline, Day 14, 21, 35
S02	Difference between treatment groups in change from baseline in Pain Disability Index at the end of the randomization phase	Continuous	MMRM	Baseline, Day 14, 21, 35
S03	Difference between treatment groups in PGI-C at the end of the randomization phase	Continuous	MMRM	Day 14, 21, 35
S04	Difference between treatment groups in change from baseline in worst pain episode measured by NPRS at the end of the randomization phase	Continuous	MMRM	Baseline, Day 14, 21, 35
S05	Difference between treatment groups in percentages of subjects with ≥ 2 point reduction from baseline in average daily NPRS score	Binary	Logistic Regression	Baseline, Day 14, 21, 35

MMRM = Mixed effects model for repeated measures

6.3.1 *Continuous Efficacy Endpoints*

Assessments are taken directly from reported CRF visits, aside from the NPRS endpoints which are only taken between treatment exposure start and end dates.

Descriptive Analyses

Summary statistics for parameter values are tabulated at select time points by treatment group (rimegepant pooled or placebo pooled).

MMRM

Treatment groups are assessed using MMRM with the following variables:

- Dependent variable: change from baseline of NPRS score averaged over each DBT period
- Fixed effects (categorical variables): treatment group, sequence, and period
- Covariate (continuous variable): baseline value of dependent variable

Random effect: subject error degrees of freedom are determined by the Kenward-Roger method.

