The following statistics are tabulated from the MMRM:

- Least-squares mean (LSMean) with corresponding SE with 95% confidence intervals (CIs) of changes from baseline by treatment group (pooled rimegepant, pooled placebo).
- Difference in LSMeans between treatment groups (pooled rimegepant, pooled placebo) with corresponding SE, and 95% CI.

6.3.2 *Continuous Efficacy Endpoints without Baseline Measurement*

Assessments are taken directly from reported CRF visits.

Descriptive Analyses

Descriptive statistics will be presented at select time points by treatment group (rimegepant pooled or placebo pooled).

MMRM

Treatment groups are assessed using MMRM with the following variables:

- Dependent variable, e.g., PGI-C score at Day 14 (note that Day is relative to the start of each treatment period)
- Fixed effects (categorical variables): treatment group, sequence, and period
- Random effect: subject error degrees of freedom are determined by the Kenward-Roger method.

The following statistics are tabulated from the MMRM:

- LSMean with corresponding standard error (SE) with 95% CIs of values by treatment group
- Difference in LSMeans between treatment groups (rimegepant, placebo) with corresponding SE, and 95% CI.

6.3.3 *Binary Efficacy Endpoints*

Assessments are taken directly from reported CRF visits, aside from the NPRS endpoints which are only taken between treatment exposure start and end dates.

Descriptive Analyses

Descriptive statistics will be presented at select time points by treatment group (rimegepant pooled or placebo pooled).

Logistic Regression

Treatment groups are assessed using Logistic Regression with the following variables:

- Dependent variable, e.g., \geq 2-point reduction in average daily NPRS score
- Fixed effects (categorical variables): treatment group, sequence, and period
- Covariate (continuous variable): baseline value of NPRS

The following statistics are tabulated from the logistic regression:

- Number and percentage of subjects with \geq 2-point reduction in average NPRS score by treatment group
- Observed percentage difference (rimegepant vs. placebo)
- Odds ratio between rimegepant and placebo with corresponding 95% CI.

6.3.4 *P01: Primary Efficacy Endpoint: NPRS*

6.3.4.1 *Main Analyses*

The NPRS is a segmented, 11-item, numeric scale ranging from 0-10. The NPRS is anchored by items ranging from “0” which represents “no pain;” to “10” which reflects “worst pain imaginable.”

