6.4.1.3 On-DBT AEs

Frequency tables of on-DBT AEs are provided for the DBT treated analysis set by SOC and PT for the following endpoints:

- AEs by intensity
- AEs related to study drug by intensity
- AEs by relationship to study drug (related, possibly related, unlikely related, not related, not reported)
- SAEs
- AEs leading to study drug discontinuation
- Exposure-adjusted multiple occurrences of unique AEs
- Hepatic-related AEs by intensity *
- Cardiovascular AEs *
- Suicidality AEs *.

AEs of special interest are asterisked ("*").

AEs with a start date on or after the first dose date/time on the Day 1 visit and prior to the first dose date/time on the Day 21 visit is considered to be in the on-DBT analysis period 1. AEs with a start date on or after the first dose date/time on the Day 21 visit to the earlier of the last dose of the DBT + 7 or the first dose of OLE - 1 is considered to be in the on-DBT analysis period 2.

Calculations for on-DB rimegepant exposure-adjusted multiple occurrences of unique AEs use an analysis period reference start date = DB rimegepant start date, analysis period reference end date = DB rimegepant last date + 7 days.

6.4.1.4 *On-OL Rimegepant AEs*

Frequency tables of on-OL rimegepant AEs are provided for the OL rimegepant treated analysis set by SOC and PT for the following endpoints:

- AEs by intensity
- AEs related to study drug by intensity
- AEs by relationship to study drug (related, possibly related, unlikely related, not related, not reported)
- SAEs
- AEs leading to study drug discontinuation

AEs with a start date on or after the first dose date/time of OL rimegepant and prior to the last dose date of the OL rimegepant + 7 is considered to be in the on-OL analysis period.

6.4.1.5 *On-DB or OL Rimegepant AEs*

On-DB or OL rimegepant AEs are provided for the DB or OL rimegepant treated analysis set by SOC and PT for the same endpoints listed in Section [6.4.1.3](#).

AEs with a start date on or after the first dose date/time of DB rimegepant or OL rimegepant and prior to the last dose date of the DB or OL rimegepant + 7 is considered to be in the on-DB or OL rimegepant analysis period.

Calculations for on-DB or on-OL rimegepant exposure-adjusted multiple occurrences of unique AEs use an analysis period reference start date = DB or OL rimegepant start date, analysis period reference end date = DB or OL rimegepant last date + 7 days.

6.4.1.6 *Post-DBT Pre-OL Rimegepant AEs*

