7.2 Analysis Periods

Analysis periods are defined as follows:

- Efficacy endpoints
 - On-DBT efficacy: This period is used to assess efficacy during the DBT Phase, and is abbreviated as “DBT” in the efficacy listing.
 - On-OL rimegepant efficacy: This period is abbreviated as “OLRMG” and used only in the efficacy listing.
 - Follow-up efficacy: This period is abbreviated as “FU” and used in the efficacy listing.
- Pretreatment characteristics and safety endpoints
 - Pretreatment: This period is abbreviated as “PRETRT” in listings, and is used to derive baseline values and to assess pretreatment safety endpoints.
 - Pre-OL rimegepant: This period is used to derive the OL rimegepant baseline value.
 - Pre-DB or OL rimegepant: This period is used to derive the DB or OL rimegepant baseline value.
 - On-DBT safety: This period is abbreviated as “DBT” in safety listings, and is used to assess safety endpoints on DBT for the DBT treated analysis set
 - Post-DBT pre-OL rimegepant safety: This period is abbreviated as “INT” in safety listings, and is used to assess safety endpoints during the interim period (i.e., post-DBT pre-OL rimegepant) for the interim treated analysis set.
 - On-OL rimegepant safety: This period is abbreviated as “OLRMG” in safety listings, and is used to assess safety endpoints for the OL rimegepant treated analysis set.
 - On-DB or OL rimegepant safety: This period is used to assess safety endpoints on DB or OL rimegepant treatment for the DB or OL rimegepant treated analysis set
 - Follow-up safety: This period is abbreviated as “FU” in safety listings, and is used to assess safety endpoints during follow-up.
- Outcomes research endpoints
 - DBT outcomes research: This period is abbreviated as “DBT” in outcomes research listings, and used to assess outcomes research endpoints during the DBT Phase
 - OL rimegepant outcomes research: This period is abbreviated as “OLRMG” in outcomes research listings, and used to assess outcomes research endpoints during the OLE Phase.

For endpoints using the “treatment strategy policy”, analysis period 1 is defined as the Day 14 CRF visit, analysis period 2 is defined as the Day 35 or Day 35/ET CRF visit.

For endpoints using the “while-on-treatment strategy”:

- For AEs, refer to Section 6.4.1 for analysis period definitions.

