- For NPRS endpoints, analysis period 1 is defined as the Day 14 visit, analysis period 2 is defined as the Day 35 or Day 35/ET visit, with visits derived using treatment exposure start and end dates.

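### SAP 7.2 assigns Penn-FPS-R, Pain Disability Index and PGI-C scores to period 2 by CRF page label alone, so an early-termination score taken before period 2 could be analysed as a period-2 outcome

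*SAP*

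**What the plan says.** SAP 3.2 handles study drug discontinuation by a treatment policy strategy for Penn-FPS-R, PDI and PGI-C: "all observed values of the endpoint of interest will be used regardless of study drug discontinuation". For endpoints under that strategy, SAP 7.2 takes period 1 from the Day 14 CRF visit, and "analysis period 2 is defined as the Day 35 or Day 35/ET CRF visit". Nothing is said about the date of the visit or whether period-2 dosing had started.

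The rules around it are tied to dates:

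- NPRS, also in 7.2: the same visit labels, but "with visits derived using treatment exposure start and end dates".
- Adverse events, SAP 6.4.1.3: period 2 takes "AEs with a start date on or after the first dose date/time on the Day 21 visit".
- Source of scores, SAP 6.3.1: "Assessments are taken directly from reported CRF visits, aside from the NPRS endpoints", which must fall between exposure start and end. SAP 6.3.2 takes PGI-C from reported CRF visits without that limit.

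The version 2.0 revision history says that analysis visit windows no longer apply. SAP 4.2 states that "all efficacy analyses will be assessed by the as-randomized treatment group", so a period-2 label brings the period-2 treatment with it. The SAP expects leavers before period 2: the disposition table in 6.2.3.1 has a row "Withdrawn from the first treatment period".

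**The concern.** Take a subject randomised to placebo then rimegepant who leaves during washout. If the ET visit is recorded on the Day 35/ET page, the 7.2 rule makes its Penn-FPS-R, PDI and PGI-C scores period-2 values. The as-randomised rule then counts them as rimegepant, although the subject has taken none. A subject who leaves in period 1 on rimegepant would have that score counted as placebo.

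Treatment policy does not justify this. It keeps scores obtained after drug is stopped; it does not move a score into a period that had not started. SAP Table 2 places these endpoints at the end of the 2-week treatment phase.

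For PGI-C there is also a conflict within the SAP. Section 6.3.2 gives the outcome as the Day 14 score and adds "note that Day is relative to the start of each treatment period". An ET visit before period 2 has no such day in period 2.

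At stake are the LSMean differences and confidence intervals of three of the five secondary efficacy endpoints (S01 to S03).

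**Working it through.** **The plan's own figure.** Protocol 9.2 and SAP 5 assume 60 randomised, 20% dropout, a paired-difference SD of 3.8, a difference of 2 and r = 0.2. Completers: 60 x 0.8 = 48. Noncentrality: 2/(3.8/√48) = 3.65. Power by the noncentral t distribution is 94.6%, which agrees with the stated value above 90%. Only r = 0.2 is used below. It is an NPRS planning value; the documents give none for these three scales, so results are shown as shares of the true difference.

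**Set-up.** Let D be the true difference and p the share of each sequence leaving before period 2, at random and equally in both sequences (assumed). The model has treatment, sequence and period terms with equal correlation r within subject; the baseline covariate is left out. With two sequences and two periods these terms fit all four cell means. The estimate is therefore the average over the two sequences of rimegepant minus placebo.

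**Washout leavers with a Day 14 record, ET filed as period 2, drug effect gone by then.**

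- Placebo-rimegepant: leavers show a difference of 0, so the sequence gives (1 − p)D.
- Rimegepant-placebo: leavers were on washout placebo, so the sequence gives D.
- Average: D(1 − p/2). The loss is p/2 at any r.

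If a fraction c of the drug effect remains in the ET score, the second sequence gives D(1 − pc), and the loss is p(1 + c)/2. SAP 6.3.5.1 gives Penn-FPS-R a past-week recall, so c above 0 is plausible; c = 0.5 is shown.

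**Period-1 leavers without a Day 14 record, ET filed as period 2.** In placebo-rimegepant the period-2 mean becomes (1 − p)D. The missing period-1 values shift the fitted period-1 mean to −rpD. The difference is D[1 − p(1 − r)], and the other sequence gives the same. The loss is p(1 − r).

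| Share leaving before period 2 | 5% | 10% | 20% |
|---|---|---|---|
| Washout, c = 0: p/2 | 2.5% | 5% | 10% |
| Washout, c = 0.5: 0.75p | 3.8% | 7.5% | 15% |
| Period 1, r = 0.2: 0.8p | 4% | 8% | 16% |
| Period 1, r = 0.5: 0.5p | 2.5% | 5% | 10% |
| Period 1, r = 0.8: 0.2p | 1% | 2% | 4% |

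The 20% column puts the plan's whole dropout allowance before period 2 and is an upper case. A date rule gives zero loss under the same assumptions.

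**Per record.** One placebo-rimegepant washout leaver among N subjects (c = 0) costs ½ x 1/(N/2) = 1/N: 5.0%, 2.5% and 1.7% at N = 20, 40 and 60.

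**The case against.** The strongest answer is that the rule may never apply.

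- **CRF page.** The CRF is not in the documents. SAP 2.1 and several protocol sections send double-blind discontinuers to the Day 119 End of Treatment visit, and SAP 6.4.2 and 6.4.5 list early termination apart from Day 35. If that page is used, nothing is mislabelled, although 7.2 then gives the score no period. This stands as a condition. Against it, 7.2 itself names a Day 35/ET visit.
- **mITT.** SAP 4.1 asks for a post-baseline efficacy assessment in each *sequence*. A subject has only one randomised order, so the natural meaning is each period. Applied by actual date, that excludes everyone who left before period 2. This too stands as a condition, but 4.1 sets no dates, and nothing stops the mislabelled ET record from counting as the period-2 assessment.
- **PGI-C.** The timing note in 6.3.2 already points against using such a score. That is fair, and it is why the two sections need reconciling.
- **Core SAP.** It governs where this SAP is silent, and 7.2 is not silent on what period 2 is. It might cover a score on the Day 119 page; it is not available to check.

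A reader might go further and infer that the primary result is biased, or that records have in fact been misfiled. The documents support neither. NPRS scores are assigned by exposure dates, and no supplied text shows a leaver before period 2 on the Day 35/ET page.

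**Conclusion.** The gap in 7.2 is real: these three endpoints lack the date condition that NPRS and adverse events have. Its effect is conditional. It needs an ET visit before period 2 recorded on the Day 35/ET page and a subject kept in mITT. If either fails, the effect is zero.

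If both hold, the LSMean difference shrinks by the amounts tabulated. The number, timing and randomness of leaving are all assumed. SAP 5 says that significance will not be evaluated, so no test is at risk; the damage is confined to descriptive secondary estimates. SAP 1 reports an early stop for low enrolment, so each such record may weigh more than it would among 60 subjects. This is a minor correction, worth making because it is cheap.

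**What to change.** Add one rule to SAP 7.2 for Penn-FPS-R, PDI and PGI-C, whatever the CRF page label:

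- An ET assessment counts as period 2 only if dated on or after the first period-2 dose.
- If dated during period 1, with no Day 14 visit, it counts as period 1.
- If dated in washout, it is listed but not used in the model.

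Reconcile the PGI-C timing note in 6.3.2 with this rule.

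Leave the mITT definition in 4.1 as it is. A sentence there refusing to count an ET record dated before period 2 would look natural. But a subject who left before any period-2 dose has no other possible period-2 record, so the sentence would remove every affected subject from mITT. SAP Table 1 uses the same population for the primary NPRS analysis, so they would be lost there too, and the 7.2 rule would have almost nothing left to act on. Relative to the label rule, the interval would widen by 2.6/5.4/11.8% for washout leavers and 1.0/2.1/4.3% for period-1 leavers at r = 0.2.

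Cost of the 7.2 rule alone, if these subjects stay in mITT: washout scores leave the model, and the variance relative to the label rule is [(1 + r)/(1 − p) + (1 − r)]/2. At r = 0.2 and p = 0.1 this is (1.2/0.9 + 0.8)/2 = 1.067, with square root 1.033. The interval widens by about 1.6/3.3/7.2% at r = 0.2, and by 2.3/4.9/10.7% at r = 0.8, when 5/10/20% leave in washout. There is no change for period-1 leavers. One residual compromise is that an early period-1 ET score stands in for an end-of-phase score; the current rule already accepts this for ET scores in period 2. The rule needs only visit and dosing dates.

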8 CONTENT OF REPORTS

The final CSR is planned after the last planned analysis.

All analyses described in this SAP are included.

9 APPENDICES

9.1 Relevant Protocol Deviations

Relevant eligibility protocol deviations include the following categories:

- A mean of < 4 on the daily “average intensity” score on the NPRS during the last 14 days in the Screening Period
- TN onset less than 3 months prior to Screening
- Classical TN not confirmed on neuroimaging
- Neurological examination not done or incomplete (i.e., cranial, facial, or trigeminal nerve assessment not done)
- Non-compliance with or inability to complete the paper diary during the Screening Period. Non-compliance is 2 or more missed evening reports during the Screening Phase. Subjects should be considered for discontinuation after discussion with the sponsor.
- Medical history, defined as any of the following subcategories:
 - Subjects with Myocardial Infarction (MI), Acute Coronary Syndrome (ACS), Percutaneous Coronary Intervention (PCI), cardiac surgery, stroke or transient focal neurological deficit during the 6 months prior to screening
 - Gilbert’s syndrome or any other active hepatic or biliary disorder
 - Gastric or small intestinal surgery.

Finding out of range during the pretreatment period or Day 35 if entering OL phase, defined as any of the following:

- ALT/AST/Direct Bilirubin/Indirect Bilirubin/Total Bilirubin > 1 xULN
- GGT > 1.5 xULN
- ECG abnormalities as follows:

- Corrected QT interval > 470 msec (QTc by method of Frederica)
- Left Bundle Branch block
- Right Bundle Branch Block with a QRS duration ≥ 150 msec
- Intraventricular Conduction Defect with a QRS duration ≥ 150 msec
- Neutrophil count $\leq 1000/\mu\text{L}$ (or equivalent)
- HbA1c $\geq 8\%$
- Diastolic measurement of $\geq 96\text{mmHg}$
- Estimated glomerular filtration rate (eGFR) according to the re-expressed abbreviated (4-variable) Modification of Diet in Renal Disease (MDRD) Study equation ≤ 40 mL/min/1.73m²
- BMI $\geq 33 \text{ kg/m}^2$
- Positive for cocaine or PCPs at any visit
- Females with a positive pregnancy test at any visit
- Subject's score is > 1 ("a little") on Question 2 or > 0 ("Not at all") on any other question on the Sheehan Suicidality Tracking Scale at any visit

Relevant subject management protocol deviations include the following:

- Type of TN discrepant between IWRS and CRF data, defined as any of the following subcategories:
 - IWRS randomization stratum of "atypical", but CRF Neuralgia type "typical" (Demographics page)
 - IWRS randomization stratum of "typical", but CRF Neuralgia type "atypical" (Demographics page)
- Prohibited non-study medications, procedures, or therapies defined as any of the following:
 - Standard of care Trigeminal Neuralgia medications with dose change or with start date < 4 weeks prior to randomization (see Section 4.4.1 for the definition of standard of care Trigeminal Neuralgia medication)
 - Carbamazepine taken during the Screening Period or afterward

- St. John's Wort taken up to 14 days prior to the Baseline Visit (randomization) or afterward
- Barbiturate-containing products (e.g. Fioricet, Fiorinal, butalbital, phenobarbital) taken up to 14 days prior to the Baseline Visit (randomization) or afterward
- Modafinil (PROVIGIL®) taken up to 14 days prior to the Baseline Visit (randomization) or afterward
- Butterbur root or extracts taken up to 14 days prior to the Baseline Visit (randomization) or afterward
- Ergotamine medications taken on ≥ 10 days per month on a regular basis for ≥ 3 months
- Narcotic medication, such as opioids, taken up to 2 days prior to the Baseline Visit or afterward
- Acetaminophen or acetaminophen containing products taken within 2 days before randomization.
- Use of acetaminophen during the Screening Period (3 to 14 days) or throughout the study at daily dosing levels of greater than 1000 mg/day
- Muscle relaxants (except baclofen) taken during the Screening Period or throughout the study
- Baclofen with start date < 8 weeks prior to randomization
- Strong CYP3A4 inhibitors taken during the Screening Period or throughout the study
- Strong CYP3A4 inducers taken during the Screening Period or throughout the study
- Strong inhibitors of the P-gp transporter taken during the Screening Period or throughout the study
- CGRP antagonists (biologic or small molecule) taken during the Screening Period or throughout the study

Note: Medications taken up to X days before a reference date or afterward are defined as those with medication start date or stop date \geq reference date $- X$. Refer to the Core SAP for additional details about prohibited non-study medications.

- DB study drug dosing issue, defined as any of the following subcategories (see Section 6.2.6):
 - DB study drug taken but not randomized
 - DB tablet count compliance < 80% from DB study drug start to later of last scheduled DBT Phase visit or DB study drug end
 - > 1 DB tablet taken on any 1 day
 - Incorrect DB study drug taken
- OLE rimegepant dosing issue, defined as any of the following subcategories (see Section 6.2.6):
 - OLE rimegepant tablet count compliance < 80% from OL rimegepant start to later of last scheduled OLE Phase visit or OL rimegepant end
 - > 1 OLE rimegepant tablet taken on any 1 day

